5.5. Method of Assessing Treatment Compliance

All drugs used for the study treatment will be administered by the Investigator or other designated study personnel. Therefore, treatment compliance will be guaranteed as long as the subject attends each visit for the administration of study treatment.

5.6. Prior, Concomitant and Prohibited Medications

Therapies used from the time the subject signs the ICF for study participation to the 40-Day F/U Visit (+ 7 days) after the last administration of U3-1402 will be recorded in the eCRF.

Prophylactic therapies (including any required premedications), prior therapies and all concomitant therapies will be recorded in the eCRF. Based on currently available clinical safety data for U3-1402, it is recommended that patients receive premedication with antiemetic agents. Refer to [Table 5.2](#).

All therapies received by subjects within 35 days prior to enrollment will be recorded as prior therapies. Concomitant therapies include all prescription, over-the-counter, and herbal remedies.

Therapies Requiring a Washout Period Before Enrollment

The following medications/therapies and products require a washout period before enrollment:

- Whole brain radiation therapy ≥ 14 days or stereotactic brain radiation therapy ≥ 7 days;
- Any cytotoxic chemotherapy, investigational agent or other anticancer drug(s) from a previous cancer treatment regimen or clinical study, ≥ 14 days or 5 half-lives, whichever is longer;
- Monoclonal antibodies other than immune checkpoint inhibitors, such as bevacizumab (anti-VEGF) and cetuximab (anti-EGFRs) ≥ 28 days;
- Immune checkpoint inhibitor therapy ≥ 21 days;
- Major surgery (excluding placement of vascular access) ≥ 28 days;
- Radiotherapy treatment to more than 30% of the bone marrow or with a wide field of radiation ≥ 28 days or palliative radiation therapy ≥ 14 days.

- Chloroquine or hydroxychloroquine >14 days

Prohibited Therapies/Products

The following medications/therapies and products will be prohibited during the Treatment Period through 40 days after the last dose of U3-1402:

- Other anticancer therapy, including cytotoxic chemotherapy, immune checkpoint inhibitors, or targeted agents
- Live virus vaccination (beginning from 28 days prior to Cycle 1 Day)
- Other investigational therapeutic agents
- Radiotherapy, except for palliative radiation (as long as the radiation field does not include a measurable lesion or does not interrupt treatment for more than 28 days from the planned date of administration [ie, 49 days from the last infusion date]). Radiotherapy to the thorax is also prohibited.
- Concomitant use of chronic systemic (IV or oral) corticosteroids (ie, >10 mg prednisone or equivalent anti-inflammatory activity) or other immunosuppressive medications except for managing AEs
- Chloroquine or hydroxychloroquine

Refer to Section [13.9](#) for further instructions.

Restricted Therapies/Products

Subjects are permitted to receive the following only when absolutely necessary:

- Investigators' discretion/clinical judgment is recommended in accordance with the institutional guidelines for the following:
 - Prophylactic or supportive treatment for expected toxicities, including management of study drug
 - Hematopoietic growth factors used for prophylaxis or treatment
 - Bisphosphonates (eg, pamidronate or zoledronate) or denosumab for pain management and palliation of bony metastases, or treatment of osteoporosis
- Subjects who wear contact lenses must discontinue wearing their lenses if they have any mild to moderate eye symptoms (CTCAE Grade ≤ 2) while receiving treatment until at least 1 week after symptoms have resolved. If a subject has a recurrence of eye symptoms or experiences any severe (CTCAE Grade ≥ 3) ocular events they must discontinue wearing their contact lenses until at least 1 week after treatment is permanently discontinued. Subjects must not use any eye drops or ointment for treatment of eye symptoms, unless agreed upon by a study doctor, at any time during the study and ≥ 1 week after permanent discontinuation of study treatment.

Permitted Therapies/Products

Subjects are permitted to receive prophylactic or supportive treatment as standard of care during the Treatment Period, per Investigator's discretion and institutional guidelines.

- Palliative radiation to known metastatic sites as long as the radiation field does not include a measurable lesion or interrupts treatment for more than 28 days from the planned date of administration (ie, 49 days from the last infusion date). Palliative radiotherapy to the thorax is permitted one week after infusion; however, the next infusion should start at least two weeks after the radiotherapy. Whenever possible, subjects should have a tumor assessment of the lesion(s) prior to receiving radiotherapy in order to rule out progression of disease. In cases of progression of disease, subjects should be discontinued from U3-1402.
- Inhaled or topical steroids or intra-articular steroid injections
- Inactive/killed virus vaccinations
- Menstruating females may receive Depo-Provera or another suppressant of menses during the entire course of study treatment. In addition, after completion of study treatment, suppression of menses should be continued until the platelet count is $\geq 50,000/\text{mm}^3$ without transfusion support
- Subjects taking warfarin should be monitored regularly for changes in prothrombin time or international normalized ratio.

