3.1.2. Duration of Subject Participation

The screening period is up to 35 days. Each cycle of treatment will be 21 days. The number of treatment cycles with U3-1402 is not limited. Subjects may continue study treatment until the time of progressive disease per RECIST v1.1, unacceptable toxicity, withdrawal of consent, death, termination of the study by Sponsor or the occurrence of any of the other events specified in Section 5.7. If PD is suspected by Investigator tumor assessment, imaging must be submitted to BICR for expedited confirmation of disease progression. The decision to discontinue U3-1402 is according to Investigator judgment and should consider BICR assessment.

Tumor assessments will be performed every 6 weeks (\pm 7 days) from Cycle 1 Day 1 for the first 24 weeks then every 12 weeks (\pm 7 days) thereafter, independent of treatment cycle, until documented disease progression by BICR per RECIST Version (v) 1.1 , death, lost to follow-up, or withdrawal of consent.

There is an End-of-Treatment (EOT) Visit that takes place within 7 days after the final dose of U3-1402 or before the start of new anticancer treatment, whichever comes first. Subjects will be asked to attend a 40-Day Follow-up (F/U) Visit (+7 days) 40 days after the last U3-1402 administration. If the subject begins another anticancer therapy before the end of the 40 days (+7 days), every effort will be made to complete all of the F/U assessments prior to starting the new therapy. For further details concerning assessments performed at the EOT and F/U Visits refer to the Schedule of Events ([Table 13.1](#)).

After discontinuation from study treatment, follow-up information for determining anti-drug antibodies (ADAs) as well as survival information and subsequent anticancer therapy, if available, should be collected every 3 months (\pm 14 days). Survival F/U contact can occur via telephone contact or unscheduled visit and will continue until death, withdrawal of consent, lost

to follow-up, or study closure, whichever occurs first. Refer to [Table 13.1](#) for details. Subjects who discontinue study treatment for any reason other than documented disease progression by BICR, death, lost to follow-up, or withdrawal of consent by the subject will continue to undergo tumor assessments at the same frequency of every 6 weeks (± 7 days) from Cycle 1 Day 1 for the first 24 weeks then every 12 weeks (± 7 days) during the follow-up period.

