6.4. End of Treatment

The EOT is defined as the date the Investigator decides to discontinue study treatment. The following EOT procedures will be performed as specified in the Schedule of Events. This visit occurs within 7 days after the final dose of U3-1402 or before the start of new anticancer treatment, whichever comes first. If the decision to withdraw/discontinue U3-1402 occurs more than 7 days after the final dose of U3-1402, then this visit should occur within 7 days after this decision or before the start of new anticancer treatment; whichever comes first. If the EOT assessments have been performed within 30 d (\pm 7 d) of their last treatment, they can be considered to be the EOT data and there is no need to repeat them; otherwise, these assessments need to be repeated. If the EOT Visit occurs \geq 40 days after the final dose of U3-1402, the 40-Day F/U Visit does not need to be conducted.

The following procedures should be obtained/Performed per the Schedule of Events (Table 13.1):

- On-treatment tumor biopsy (optional) (Section 8.3.2). An optional EOT on-treatment tumor biopsy will also be performed at the time of progression or discontinuation from study treatment with minimal 2 cores or 20 slides (if provided as slides). Consent for this biopsy should be documented in the tissue consent portion of the appropriate ICF. Tumor biopsy should be obtained from primary tumor or metastatic site, preferably from a site of recent radiographic progression, within 40 days of the last dose of U3-1402, and prior to starting any new anticancer treatment.
- Collect urine for urinalysis (Section 9.8).
- Obtain a serum or urine sample for pregnancy testing in women of childbearing potential within 72 hours of enrollment for all female subjects of childbearing potential. A positive urine pregnancy test result must immediately be confirmed using a serum test. Perform repeat pregnancy tests (urine or serum test per institutional guideline) 72 hours before infusion of each cycle and at end of treatment.
- Complete physical examination and record weight (Section 9.11).
- Vital signs (Section 9.9). Assessments will include systolic and diastolic blood pressure, pulse rate, respiratory rate, and body temperature. Blood pressure and pulse rate should be measured after the subject has rested in a supine position for 5 minutes.
- Perform SpO₂ (Section 9.12). When CT/MRI is conducted, SpO₂ should also be obtained per Investigator discretion.

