- Assess functional status using the ECOG PS Scale (Section 13.6).
- Obtain blood samples for the following:
 - Safety laboratories (Section 9.8);
 - Biomarkers (Section 8.3);
 - CEA, CA 19-9, CRP (Section 9.8);
 - ADA (Section 8.4);

- PK analysis (Section 8.1). PK assay can be performed on the ADA sample collected.
- LVEF measured by ECHO or MUGA. The same test must be used for the subject at screening, EOT, and as clinically indicated. (Section 9.12).
- Perform a 12-lead ECG. Subjects should rest supine for at least 10 minutes prior to the ECG assessment. The same test must be used for screening, EOT, and as clinically indicated (Section 9.10).
- Ophthalmologic assessments include visual acuity test (ETDRS, Snellens, or Landolt), slit lamp examination, fundoscopy, and tonometry. A 40 +7-Day F/U assessment is only required if an on-treatment assessment was abnormal at the time of discontinuation of study therapy, to confirm reversibility of the abnormality.
- AEs/SAEs assessment and review concomitant medications (Section 9).

6.5. 40-day Post-treatment Follow-up

Assessments to monitor ongoing safety, and immunogenicity in the follow-up period will be performed 40 days (+7 days) after the last dose of U3-1402 or before starting new anticancer treatment, whichever comes first. For detailed explanations of the timing and nature of assessments performed, refer to the Schedule of Events (Table 13.1).

- Perform tumor assessment by CT or MRI scans of the brain (if stable brain metastasis was present at baseline), chest, abdomen, pelvis, and any other sites of disease every 6 weeks (\pm 7 days) from Cycle 1 Day 1 for the first 24 weeks then every 12 weeks (\pm 7 days) thereafter, independent of treatment cycle, until documented disease progression by BICR per RECIST v1.1, death, lost to follow-up, or withdrawal of consent.
- Obtain a serum or urine sample for pregnancy testing in women of childbearing potential within 72 hours of enrollment for all female subjects of childbearing potential. A positive urine pregnancy test result must immediately be confirmed using a serum test.
- Complete physical examination and record weight (Section 9.11).
- Vital signs (Section 9.9). Assessments will include systolic and diastolic blood pressure, pulse rate, respiratory rate, and body temperature. Blood pressure and pulse rate should be measured after the subject has rested in a supine position for 5 minutes

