11.5.2. Safety Analyses

Safety analyses will be performed using the Safety Analysis Set and in general will be descriptive. Additional details regarding safety analyses will be described in the SAP.

The overall study period will be divided into three mutually exclusive segments:

- Pre-treatment period: from date of study informed consent (inclusive) to the start date of study treatment – 1;
- On-treatment period: from the start date of study treatment (inclusive) to 47 days after the end date of study treatment (inclusive);
- Post-treatment period: starting from 48 days after the end date of study treatment.

Safety summaries will include assessments collected during the on-treatment period unless otherwise specified. Data will be summarized by cohort if applicable. All assessments will be listed.

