13.2.9. Protocol Deviations

The Investigator should conduct the study in compliance with the protocol agreed to by the Sponsor and, if required, by the regulatory authority(ies), and which was given approval/favorable opinion by the IECs/IRBs.

A deviation to any protocol procedure or waiver to any stated criteria will not be allowed in this study except where necessary to eliminate immediate hazard(s) to the subject.

The Sponsor must be notified in writing of all intended or unintended deviations to the protocol (eg, inclusion/exclusion criteria, dosing, missed study visits) within 24 hours and in accordance with the clinical study agreement between the parties.

The Investigator, or person designated by the Investigator, should document and explain any deviation from the approved protocol.

If a subject was ineligible or received the incorrect dose or study treatment, and had at least one administration of study drug, data should be collected for safety purposes.

If applicable, the Investigator should notify the IEC/IRB of deviations from the protocol in accordance with local procedures.

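### Section 5.6 bars other anticancer therapy through day 40 after the last dose, yet the visit sections are timed as if it may start sooner, and the 47-day TEAE window does not separate events that follow it

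*Combined protocol and SAP*

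**What the plan says.** **The prohibition.** Section 5.6 (Prohibited Therapies/Products) opens with "The following medications/therapies and products will be prohibited during the Treatment Period through 40 days after the last dose of U3-1402". Its first item is "Other anticancer therapy, including cytotoxic chemotherapy, immune checkpoint inhibitors, or targeted agents". Nothing exempts a subject who has progressed or has permanently stopped U3-1402.

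**The visit sections.**
- Section 3.1.2, on the 40-day visit: "If the subject begins another anticancer therapy before the end of the 40 days (+7 days), every effort will be made" to finish the follow-up assessments before the new therapy.
- Section 6.4, on the end-of-treatment (EOT) visit: "This visit occurs within 7 days after the final dose of U3-1402 or before the start of new anticancer treatment, whichever comes first". Table 13.1 footnote a says the same.
- Section 6.5 sets the 40-day visit at day 40 (+7) "after the last dose of U3-1402 or before starting new anticancer treatment, whichever comes first". Table 13.1 footnote b says the same.

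None of these refers to Section 5.6 or describes a start before day 41 as a deviation.

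**Deviations.** Section 13.2.9 states "A deviation to any protocol procedure or waiver to any stated criteria will not be allowed in this study". It then excepts what is needed to remove an immediate hazard to the subject. Deviations must be notified to the sponsor in writing within 24 hours.

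**Safety analysis.** Section 11.5.2 defines "On-treatment period: from the start date of study treatment (inclusive) to 47 days after the end date of study treatment (inclusive". Section 11.5.2.1 counts as a TEAE any adverse event that starts or worsens in that period. Neither section has a cut or a flag at the start of new anticancer therapy. Section 11.5.2 leaves further detail to the SAP.

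**The concern.** Two issues meet in the weeks after the last dose.

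The first is the rule itself. Section 5.6 alone tells a site that no other anticancer therapy may begin until after day 40. The visit sections suggest that it may begin earlier, provided assessments are done first. About 40 sites may settle this differently. They may also differ on whether a start before day 41 is a deviation to be reported within 24 hours.

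The second is what the safety tables then contain. Table 2.1 makes TEAEs and other safety parameters a primary outcome measure, although the objective is secondary. AESI and on-treatment death summaries use the same window. If new therapy begins inside the window, its toxicity enters the U3-1402 tables, and how much enters could depend on how each site read the rule.

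**Working it through.** **Step 1: what each visit clause can do if Section 5.6 is obeyed.** Day *n* means *n* days after the last dose. The ban covers day 40, so the earliest compliant start is day 41.

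| Clause | When it has effect | Room left under Section 5.6 |
|---|---|---|
| Section 3.1.2, new therapy before the end of day 40 (+7) | Start on days 1 to 47 | Days 41 to 47 only |
| Section 6.4 and footnote a, EOT visit within 7 days of the final dose or before new treatment | Start within about a week of the final dose | None |
| Section 6.4, decision to stop made more than 7 days after the final dose: visit within 7 days of the decision or before new treatment | Start within 7 days of a decision on day *d* | Only if *d* + 7 ≥ 41, that is *d* ≥ 34 |
| Section 6.5 and footnote b, 40-day visit or before new treatment | Start before the visit at day 40 (+7) | Days 41 to 47 only |

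A decision on day 34 or later is possible, because Section 5.4.1.1 lets dosing be delayed to 49 days from the last infusion. So part of the wording fits Section 5.6. The basic EOT clause does not: its new-treatment limb matters only if treatment begins well inside the prohibited period. The 40-day clause keeps only a seven-day remnant.

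The optional EOT biopsy points the same way. Section 6.4 and Table 13.1 footnote f require it within 40 days of the last dose and also before any new anticancer treatment. If none can start by day 40, the second condition adds nothing.

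**Step 2: overlap with the TEAE window.** The inputs are the 47-day limit (Section 11.5.2; Section 9.2 uses the same limit for collecting adverse events) and a start day *s*. The end date of study treatment is taken to be the date of the last dose. The documents give no distribution of start times, so every *s* below is an assumption.

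Overlap in days = 47 − *s* + 1, counting the start day.

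| Assumed start | Overlap | Share of 47 days |
|---|---|---|
| Day 8 | 47 − 8 + 1 = 40 | 85% |
| Day 14 | 47 − 14 + 1 = 34 | 72% |
| Day 21 | 47 − 21 + 1 = 27 | 57% |
| Day 28 | 47 − 28 + 1 = 20 | 43% |
| Day 41 (first compliant day) | 47 − 41 + 1 = 7 | 15% |

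The last row shows that the TEAE issue does not depend on the contradiction. Full compliance with Section 5.6 still leaves up to seven days in which events on new therapy count as TEAEs.

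**Step 3: what is not touched.** The rates in Table 11.2 (97.4% and 2.0% for 8 of 68; 98.7% and 1.8% for 9 of 80) reproduce by exact binomial calculation and do not depend on this point. Nor do the interim rules.

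**The case against.** The best defence is that a prohibition and a contingency plan can coexist. No visit section permits or directs an early start; Section 3.1.2 is conditional and the others only schedule visits. This stands in part. A reader might infer that sites are given opposite instructions and cannot satisfy both, but a site that waits until day 41 complies with every passage. What remains is that the contingency is written as routine scheduling, is never called a departure, and in the EOT clause has almost no other use.

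It can also be said that attribution is already handled. Section 9.4.4 has the investigator weigh concomitant medications when judging causality, and Section 11.5.2.1 tabulates drug-related TEAEs separately. Safety is descriptive, with one treatment and no formal cohort comparison. Further rules are left to the SAP, and no separate SAP text was available in the document reviewed. This is real mitigation. It does not replace a split by date, because relatedness is a judgement made in an open-label study and the all-cause TEAE tables remain mixed.

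Three further inferences are not supported:
- **Most subjects are affected.** Progression accounted for 74 of 94 discontinuations (79%) in J101 and 20 of 24 (83%) in U102, which scaled to 80 subjects gives 63 to 67. Those are breast cancer and NSCLC studies, and the counts are of progression, not of new therapy started within 40 days. In J101, 50 subjects were still on drug. Section 1.1.1 names only two approved later-line agents, so prompt uptake cannot be assumed.
- **Next-line therapy is held back by a fixed 19 days (40 − 21), with 26 days (47 − 21) of mixed safety data.** This needs an undelayed last dose, a scan exactly on the next planned Day 1, and new therapy ready that day. Scans have a ±7-day window, unscheduled scans and dose delays are allowed, and suspected progression goes to BICR.
- **Section 13.2.9 allows no deviation at all.** It excepts immediate hazards.

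**Conclusion.** The inconsistency is in the text. Section 5.6 prohibits what Sections 3.1.2, 6.4 and 6.5 and Table 13.1 footnotes a and b make arrangements for. Days 41 to 47 and late EOT decisions explain only part of that wording. The consequence is room for sites to differ on the rule and on what is reportable. It has not been shown that they will differ.

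The TEAE point is separate and holds under either reading: any start before day 48 puts events on the new therapy into the U3-1402 TEAE count. Contamination is possible, not established, and its size cannot be estimated from the documents. The overlaps shown are illustrations that rest on assumed start days and on the treatment end date being the last-dose date.

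Severity is moderate. The point bears on safety attribution and deviation reporting. It does not change ORR, the sample size or the interim decisions.

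**What to change.** 1. Reconcile Section 5.6 with Sections 3.1.2, 6.4 and 6.5 and Table 13.1 footnotes a and b, so that one statement governs other anticancer therapy from the last dose to day 40 (+7) and says whether a start in that period is a deviation under Section 13.2.9. Which rule is right is a clinical decision that this review does not make.
2. In Section 11.5.2.1 or the SAP, keep the TEAE definition and add a supplementary TEAE summary that separates events with onset on or after the start of new anticancer therapy.

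The cost is a wording change and one extra table. No new data should be needed: Section 5.6 records therapies to the 40-day visit (+7 days), and Section 6.6 and Table 13.1 cover new anticancer treatment in follow-up. The team should confirm that the start date is captured. The downside is slightly less follow-up in the separated summary, which is why it should supplement the main TEAE table and not replace it.

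### Section 5.6 both prohibits and permits palliative radiotherapy to the thorax during the Treatment Period

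*Combined protocol and SAP*

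**What the plan says.** Section 5.6 sets out concomitant therapy in separate lists. Two of them deal with radiotherapy while the subject is on study drug.

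- **Prohibited Therapies/Products.** The items listed are "prohibited during the Treatment Period through 40 days after the last dose of U3-1402". The radiotherapy bullet bars radiotherapy, excepts palliative radiation subject to conditions on the field and on treatment interruption, and then adds: "Radiotherapy to the thorax is also prohibited". That last sentence has no palliative exception and no timing condition.
- **Permitted Therapies/Products.** The list opens with "Subjects are permitted to receive prophylactic or supportive treatment as standard of care during the Treatment Period". Its first bullet allows "Palliative radiation to known metastatic sites as long as the radiation field does not include a measurable lesion", together with a limit on treatment interruption. It continues: "Palliative radiotherapy to the thorax is permitted one week after infusion; however, the next infusion should start at least two weeks after the radiotherapy". The bullet also asks for a tumor assessment before radiotherapy where possible, and says "In cases of progression of disease, subjects should be discontinued from U3-1402".

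Section 13.2.9 sets the rule for departures from the protocol: "A deviation to any protocol procedure or waiver to any stated criteria will not be allowed in this study", except where necessary to eliminate an immediate hazard. The Sponsor must be told in writing of all "intended or unintended deviations to the protocol (eg, inclusion/exclusion criteria, dosing, missed study visits) within 24 hours".

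**The concern.** Two instructions in one section give opposite answers on whether a subject on treatment may have palliative thoracic radiotherapy. The study is planned for about 40 sites in the United States, Europe and Asia (Section 3.1). Sites may therefore differ in what they do. They may also differ in whether they record it as permitted care or report it as a deviation, so deviation data on this point would not be comparable between sites.

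The subject is safety-relevant on the protocol's own terms. Section 9.3.1 treats ILD as an important identified risk, and exclusion criterion 1 in Section 4.2 counts radiation pneumonitis within a history of ILD. A rule on irradiating the chest during treatment should have only one reading.

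**Working it through.** The point rests on text, and the plan gives no figure to reproduce. The check is whether the two bullets can be read so that both hold.

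| | Prohibited list | Permitted list |
|---|---|---|
| Period | Treatment Period, and on to 40 days after the last dose | Treatment Period |
| Palliative radiation in general | Allowed under conditions on field and interruption | Allowed at known metastatic sites under conditions on field and interruption |
| Radiotherapy to the thorax | Prohibited, no exception stated | Palliative use permitted, timed around infusions |

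**1. Do the lists cover different times?** No. Both name the Treatment Period. The permission is also framed between infusions: one week after one infusion, and at least two weeks before the next. The shortest such interval is 7 + 14 = 21 days, which is one treatment cycle. The permission therefore operates while the subject is on treatment, wholly inside the period of the prohibition. Dose delays under Section 5.4.1.1 can lengthen the interval but do not move it outside that period.

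**2. Could the thorax ban reach only non-palliative radiotherapy?** The preceding sentence of the same bullet already bars non-palliative radiotherapy at every site, because its only exception is for palliative radiation. If the thorax sentence covered non-palliative treatment alone, it would add nothing. It has an effect only if it reaches palliative thoracic radiotherapy, which is what the Permitted list allows.

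**3. Does any other text settle the matter?** No. Neither bullet refers to the other, and no section says that one list overrides the other. The Summary of Changes entries touching Section 5.6 concern topical steroids, antibody washout, the screening period and the corticosteroid wording. None mentions thoracic radiotherapy.

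**4. Who is affected?** Subjects who need palliative thoracic radiotherapy during treatment and otherwise meet the Permitted bullet: a known metastatic site, its measurable-lesion condition, and its limit of 28 days' interruption from the planned dose. Subjects found to have progressed would mostly fall outside, since the bullet says they should stop study drug. That limit is not absolute, because Section 5.7 lets a subject who meets a discontinuation criterion continue with Sponsor approval.

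**5. Does it reach the primary analysis?** No such effect is shown. Section 11.4 defines the Full Analysis Set as all subjects given at least one dose, and no text removes a subject for prohibited radiotherapy.

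**The case against.** The best defence is that the permission is a specific exception to a general ban. The ban speaks of thoracic radiotherapy at large, while the permission is limited to palliative use and timed around infusions. A site that follows an express, conditional permission in the same section has a textual basis for calling its conduct compliant. Redundancy in the ban does not rule this reading out, because Section 5.6 repeats itself elsewhere.

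That reading is available, but the text does not require it. The Prohibited bullet states its palliative exception first and adds the thorax sentence after it, so a site could as reasonably take that sentence as a limit on the exception. With two defensible readings and no stated precedence, the deviation status of the act depends on which list is applied.

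It is also fair to say that the safety link is indirect. Exclusion criterion 1 is an eligibility rule, and no text explains why thoracic radiotherapy is restricted. Suspected ILD leads to a dosing delay and work-up under Table 5.2 and Section 9.3.1, and potential cases go to adjudication under Section 9.3.1.1, whichever bullet a site follows. Differing conduct between sites is an inference from the wording. These points lessen the consequence but do not remove the contradiction.

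**Conclusion.** The concern holds. For palliative thoracic radiotherapy that meets the Permitted bullet, the two instructions cannot both be followed as written, and judged by the Prohibited list alone, use of the permission is a deviation.

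The size is limited. The number of subjects affected is not stated and cannot be derived from the documents. No effect is claimed on ORR, the interim decision rule or the sample size. What is at stake is uniform site conduct and consistent classification of deviations, on a topic close to an important identified lung risk. That merits correction but does not threaten the primary analysis. The conclusion rests only on the wording of the two bullets, the periods stated for the two lists, and the absence of any text giving one list precedence.

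**What to change.** Reconcile the two bullets in Section 5.6 into a single rule on radiotherapy to the thorax, with its period stated. Write it once, or place it in one list with a cross-reference from the other. Which rule applies is a clinical decision for the sponsor, and this review takes no view on it.

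The same edit should align the general palliative conditions. Read literally, the Prohibited bullet joins the field and interruption conditions so that meeting either would suffice, while the Permitted bullet appears to require both.

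The cost is a change of wording in two bullets, carried in a protocol amendment that needs written IRB or IEC approval under Section 13.2.1. It could travel with another amendment, such as the one Section 11.6 requires before Cohort 2 enrolls further, but need not wait for it. Sample size, endpoints, analysis sets and the Schedule of Events stay as they are.
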